1. PROTOCOL SUMMARY

1.1 Executive Synopsis

Rationale for Proposed Clinical Study

In December 2019 the Wuhan Municipal Health Committee identified an outbreak of viral pneumonia cases of unknown cause. Coronavirus ribonucleic acid (RNA) was quickly identified in some of these patients. As of July, 2020 there were 15.5 million confirmed cases (>4 million in the US) and over 600,000 deaths (~145,000 in the US). There are currently no FDA approved prophylactic interventions against SARS-CoV-2 while social distancing and personal protective equipment constitute our only viable countermeasures to help reduce the incidence of community transmission. While vaccine candidates are being developed at unprecedented speeds, their efficacy is completely unknown and will not be known for many months.

Therefore, there is an urgent public health need for rapid development of novel protective measures, as well as improved therapeutic interventions. The EmitBio™ RD19 device emits visible blue light to stimulate host defenses (as explained below) to eliminate invading pathogens in the oropharynx and surrounding tissues. The RD19 device does this without additional photosensitizers or chemical reagents that are typically employed with traditional photodynamic therapeutics. Specifically, selected wavelengths of light have been evaluated across the visible spectrum, and it was discovered that safe, visible blue light emitted from non-coherent LED sources could perform both of the following functions:

- (1) upregulate the sustained production of nitric oxide in epithelial tissue through increase of nitric oxide synthases (NOSs);

- (2) stimulate the instantaneous release of the body's bound stores of nitric oxide.

Nitric oxide produced naturally in epithelial tissues also induces and recruits effector cells of the innate immune system, including natural killer (NK) cells, neutrophils and macrophages to phagocytize virus-infected cells at the site of primary infection.

1.1.1 Claims and Indication:

The EmitBio™ RD19 device uses blue light to boost the body's natural immune response, which when combined with social distancing and proper mask use as part of healthy living, may help to reduce the risk of infection by respiratory viruses like influenza and SARS-CoV-2.

This first-in-man (FIM) phase I study will evaluate the acute safety, tolerability, device acceptability for use among 25 healthy volunteers between the age of 18 and 45. Based on the results of extensive in-house research, a single dose (9 Joules/cm²) and schedule (twice a day for 3 minutes, separated by at least 4 hours, ideally 8 to 12 hours apart) will be evaluated.

Safety and tolerability (local reactogenicity) will be assessed actively at study day screening (baseline set), 1, 7 and 14, and on non-clinic visit days by collection of these data by history during clinic visits via a memory aid (diary cards). Volunteers will be encouraged to contact designated clinical trial staff for AEs of a medically-urgent nature as soon as is practically possible and to seek immediate medical care, if needed.

Metabolic, liver and kidney safety laboratory evaluations, as well as urinalysis, will be performed at screening and at Day 14 or early termination (and potentially during unscheduled) clinic visits. Hematological safety assessments will be performed at all visits.

1.1.2 Objectives and Endpoints

Table 1: Objectives and Endpoints (Outcome Measures)

| OBJECTIVES | ENDPOINTS (OUTCOME MEASURES) |
|------------|--|
| Primary | 
Evaluation of the safety and reactogenicity of the RD19 device. 
Frequency, grade and attribution of each incident local and systemic AE during the 14 day study period.Frequency and attribution of any incident SAEs during the 14 day study period. |
| Secondary | 
Evaluation of the acceptability of the EmitBio™ RD19 device. 
Ease of use, clarity of user instructions, & compliance with per protocol schedule and, if out of compliance, reason(s) for non-compliance. |

1.1.3 Inclusion Criteria (abbreviated)

See full inclusion criteria in Section 4.1

A subject must meet all the following criteria to be eligible to participate in this study:

1. Provides written informed consent prior to initiation of any study procedures.
2. Be able to understand and agrees to comply with planned study procedures and be available for all study visits.
3. Agrees to the collection of venous blood per protocol.
4. Male or non-pregnant female, 18 to 45 years of age, inclusive, at time of enrollment.
5. Body Mass Index 18-35 kg/m², inclusive, at screening.
6. No active disease process (chronic or acute) or physical or mental conditions or attributes at the time of screening, which in the opinion of the PI, will prevent full use and assessment of RD19.
7. Oral temperature is less than 100.0°F (37.8°C).
8. Pulse no greater than 90 beats per minute.
9. Systolic blood pressure (BP) is 85 to 150 mmHg, Diastolic blood pressure (BP) is ≤ 90, inclusive.
10. Clinical screening laboratory evaluations are within acceptable normal reference ranges at the clinical laboratory being used in the study

Exclusion Criteria (abbreviated)

See full exclusion criteria in Section 4.2

A subject who meets any of the following criteria will be excluded from participation in this study:

1. Positive urine pregnancy test at screening.
2. Has any medical disease or condition that, in the opinion of the site Principal Investigator (PI) or appropriate sub-investigator, precludes study participation.
3. Presence of self-reported or medically documented significant medical or psychiatric condition(s).
4. Has an acute illness, as determined by the site PI or appropriate sub-investigator, with or without fever [oral temperature >37.8°C (100.0°F)] within 72 hours prior to screening.
5. Has participated in another investigational study involving any SARS-CoV-2/COVID-19 interventional investigational product within 30 days of screening.
6. Has a history of hypersensitivity or severe allergic reaction (e.g., anaphylaxis, generalized urticaria, angioedema, other significant reaction) to nitrates, nitrates or sun exposure.

1.1.4 Study Key Characteristics

Study Phase

- I

Study Population

- Twenty-five (25) males and non-pregnant females, 18 to 45 years of age, inclusive, who are in good health and meet all eligibility criteria will be enrolled.

Sites

- Carolina Phase I, Raleigh, NC

RD19 Device

- The EmitBio™ RD19 device emits visible blue light to stimulate host defenses (as explained below) and eliminate invading pathogens in the oropharynx and surrounding tissues. The RD19 device does this without additional photosensitizers or chemical reagents that are typically employed with traditional photodynamic therapies. Specifically, selected wavelengths of light have been evaluated across the visible spectrum, and it was discovered that a narrow wavelength band blue light emitted from non-coherent LED sources could perform both of the following functions: upregulate the sustained production of nitric oxide in epithelial tissue through the increase of NO synthases (NOSs); and stimulate the instantaneous release of the body's bound stores of nitric oxide. Nitric oxide also induces and recruits effector cells of the innate immune system, including natural killer (NK) cells, neutrophils and macrophages to phagocytize virus-infected cells at the site of primary infection.

Table 2: Treatment Group

| Group | RD19 | Duration |
|-------|------|------------|
| OL | 25 | 3' x 2/day |

Study Duration

- The duration of the entire study is anticipated to be \leq 18 days (from start of screening to last subject last visit).

Subject Duration

- The duration on trial for each individual subject is \leq 18 days (from start of screening to last visit).

Safety

- The study will use study pausing rules
- This study will involve the Sponsor's Chief Medical Officer as medical monitor, who along with the study PI(s) will assess severe AEs and SAEs, and together will constitute the attribution team.

1.2 Schedule of Activities (SOA) - Table 3

| Study Procedures | Screening Visit | Preliminary Observation | Full Assessment Period | |
|------------------------------------|-----------------|---|---|---|
| Study Day | ≤ -7 to 0 | 1 | 7 | Day 14/ Early Term |
| Study Procedures | | | | |
| Informed Consent | X | | | |
| Inclusion/Exclusion Criteria | X | X | | |
| Demographics Questionnaire | X | | | |
| Medical History | X | * Changes since last visit only | *Changes since last visit only | *Changes since last visit only |
| Physical Examination | X | *Targeted only | *Targeted only | *Targeted only |
| BMI | X | | | |
| Vital Signs | X | X | X | X |
| Methemoglobin | X | *Before and 60 minutes after device use | *Before and 60 minutes after device use | *Before and 60 minutes after device use |
| Lab Sample Collection & Processing | X | | | X |
| CBC and differential | X | | | X |
| CMP | X | | | X |
| Urinalysis | X | | | X |
| Urine Pregnancy Test | X | | | X |
| Concomitant Medication History/New | X | X | X | X |
| Device Illumination | | X | X | X |
| Acceptability Assessment of Device | | X | X | X |
| Distribution and train diary card | | X | | |

2. INTRODUCTION

2.1 Background and Study Rationale

In December 2019 the Wuhan Municipal Health Committee identified an outbreak of viral pneumonia cases of unknown cause. Coronavirus RNA was quickly identified in some of these patients. This novel Coronavirus (nCoV) has been abbreviated as 2019-nCoV and is now named SARS-CoV-2 (due to its similarity to the Severe Acute Respiratory Syndrome [SARS] Coronavirus [CoV; SARS-CoV]). It has 89% nucleotide identity with bat SARS-like-CoVZXC21 and 82% with that of human SARS-CoV (Chan JF et al., 2020). The disease caused by SARS-CoV-2 is called Coronavirus disease 2019 (COVID-19). As of July, 2020 there were 15.5 million confirmed cases (> 4 million in the US) and over 600,000 deaths (~145,000 in the US). There are currently no FDA approved prophylactic interventions against SARS-CoV-2 while social distancing and personal protective equipment constitute our only viable countermeasures to help reduce the incidence of community transmission. While vaccine candidates are being developed at unprecedented speeds, their efficacy is completely unknown and will not be known for many months. Outbreak forecasting and modeling suggest that these numbers will continue to rise. Global efforts to evaluate novel antivirals and therapeutic strategies to treat 2019-nCoV severe infections have intensified.

Therefore, there is an urgent public health need for rapid development of novel protective measures, as well as improved therapeutic interventions. The EmitBio™ RD19 device emits visible blue light to stimulate host defenses and eliminate invading pathogens in the oropharynx and surrounding tissues. The RD19 device does this without the additional photosensitizers or chemical reagents that are typically employed with traditional photodynamic therapy approaches. Specifically, selected wavelengths of light have been evaluated across the visible spectrum, and it was discovered that a narrow wavelength band blue light emitted from non-coherent LED sources could perform both of the following functions: upregulate the sustained production of nitric oxide in epithelial tissue through the increase of NO synthases (NOSs); and stimulate the instantaneous release of the body's bound stores of nitric oxide. Nitric oxide also induces and recruits effector cells of the innate immune system, including natural killer (NK) cells, Neutrophils and Macrophages to phagocytize virus-infected cells at the site of primary infection.

2.1.1 EmitBio™ RD19 Device Characteristics:

| Characteristic | Target |
|--------------------------------------|--|
| Route of Administration | Oral Illumination |
| Device Configuration | Hand-held, rechargeable |
| Blue Light Source | Non-coherent, light emitting diode (LED) array |
| UVA Content (315 nm – 400 nm) | <1% |
| UVB Content (280 nm - 315 nm) | not detectable* |
| UVC Content (100 nm - 280 nm) | not detectable* |
| Target Exposure Area | Oropharynx and surrounding tissues |
| Exposure Time | 3 min per treatment, 2X/day at least 4 hrs apart |
| Single Light Dose (@ 90 mm) | ~ 9 J/cm ² Joules = Watts x seconds |
| Total Daily Dose (@ 90 mm) | ~ 18 J/cm ² |
| Depth of Tissue Penetration | < 0.5 mm |
| Temperature (IEC 60601-1) | < 48 °C (for durations <10 min) |

*UVA/UVB not detectable in Labsphere 1M Integrating Sphere equipped with CDS-610 Mini CCD Array Spectrometer

2.2 Risk/Benefit Assessment

2.2.1 Known Potential Risks

The potential risks of participating in this trial are those associated with having blood drawn and unlikely, but possible, mild local reactions to the EmitBio™ RD19, entirely unknown adverse events, and inadvertent breach of confidentiality.

Drawing blood may cause transient discomfort and fainting. Fainting is usually transient and managed by having the subject lie down and elevate his/her legs. Bruising at the blood draw site may occur but can be prevented or lessened by applying pressure to the blood draw site for a few minutes after the blood is taken.

Extensive evaluation of the RD19 and similar energy-based devices routinely used for oral and skin care purposes have resulted in the Sponsor, after careful consideration, making the determination that RD19 as a “Not Significant Risk” (NSR) device per FDA guidelines.

EmitBio™ RD19 is expected to be without significant risk for acute adverse events when used as directed. If the RD19 device is not used as directed, for example is inserted into the oral cavity improperly it is possible the user could induce a gag reflex. If the RD19 device is used for a period of time in excess of the time directed, it is possible the user could experience mild to moderate erythema, and under extreme overuse conditions the user could experience oral mucosal thermal injury, especially to the uvula.

Eye exposure is to be avoided. Direct illumination of unprotected eyes can result in damage to the retina, and especially the macula. Other eye structures can also experience thermal injury. Study staff must ensure volunteers understand to never point the RD19 device toward their or anyone else's eyes.

Risks to Privacy: Subjects will be asked to provide personal health information (PHI). All attempts will be made to keep this PHI confidential within the limits of the law. However, there is a chance that unauthorized persons will see the subject's PHI. All study records will be kept in a locked file cabinet or maintained in a locked room at the participating clinical trial site(s). Electronic files will be password protected. Only people who are involved in the conduct, oversight, monitoring, or auditing of this trial will be allowed access to the PHI that is collected. Any publications from this trial will not use information that will identify subjects by name. Organizations that may inspect and/or copy research records maintained at the participating clinical trial site(s) for quality assurance (QA) and data analysis include groups such as the IRB and the FDA.

A description of this clinical trial will be posted on <http://www.ClinicalTrials.gov>. This web site will not include information that can identify subjects.

There may be other risks, discomforts or side effects that are entirely unknown at this time.

2.2.2 Known Potential Benefits

There is no guaranteed benefit to study participants. There is the potential for benefit to society resulting from insights gained from participation in this study due to the widespread, and accelerating, threat of SARS-CoV-2 and COVID-19. Use of EmitBio™ RD19 may or may not provide protection against SARS-CoV-2 infection and subsequent COVID-19 disease.

3. STUDY DESIGN

3.1 Overall Design

This first-in-man (FIM) phase I study will evaluate the acute safety, tolerability, and device acceptability for use among 25 healthy volunteers between the age of 18 and 45. Based on the results of numerous preclinical studies, a single dose (9 joules/cm²) and schedule (twice a day, separated by at least 4 hours, preferably 8 to 12 hours apart) will be evaluated.

Safety and tolerability (local reactogenicity) will be assessed actively at the following study days: screening (baseline set), 1, 7 and 14, and on non-clinic visit days by collection of these data by history during clinic visits via a memory aid (diary cards). Volunteers will be encouraged to promptly contact designated clinical trial staff or the one of the Sponsor's Emergency Response Team for AEs of a medically urgent nature.

A Comprehensive Metabolic Panel, as well as CBC with differential, urinalysis, and pregnancy testing will be performed at screening and at Day 14 or early termination (and potentially during unscheduled) clinic visits. Hematological safety assessments (evaluation of methemoglobinemia) will be performed at all visits.

Study volunteers will be asked to immediately contact the clinical coordinator and/or the PI in all instances where they experience an AE of greater than moderate intensity. Volunteers will be instructed to report to the clinical trial unit for an unscheduled visit or to seek the appropriate level of medical care based on the nature of their AE/SAE. In all such instances, all relevant information pertaining to these significant medical events will be captured on the appropriate e-CRFs.

Hematology safety laboratory evaluations will be performed at screening, as well during all scheduled clinic visits. Laboratory assessments may be part of the evaluation of medically attended AE evaluation and for all SAEs.

Upon ratification of the CTA, the site will begin pre-recruitment outreach efforts of potential volunteers within M3-WRA's database to ascertain "interest in general" in this study. Official recruitment which may include fliers, letters, telephone calls, etc. and specific recruitment of potential subjects who have previously participated in other clinical studies conducted at the site will occur only after formal IRB approval. Other forms and/or mechanisms of recruitment may also be used. The IRB will approve the recruitment process and all materials prior to use.

Schedule of assessments can be found in Section 1.2, Schedule of Activities (Table 3).

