4.3.2 Retention

Study retention strategies will include education and explanation of the study schedule and procedures during screening and enrollment visits and restriction of enrollment to persons who can attend all study visits. Participating subjects will be reminded of subsequent visits during each visit, and study staff will contact subjects prior to appointments. Study staff will contact subjects who miss appointments to encourage them to return for completion of safety evaluations.

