5.5 Device Discontinuation

5.5.1 Study Pausing Criteria

RD19-01-3Q20 will be paused if any of the following events occur:

- Any subject experiences an SAE after use of the RD19 Device that is considered related to RD19.
- Any subject experiences laryngospasm, bronchospasm or anaphylaxis within 2 hours after use of the RD19 Device that is considered related to RD19.
- Two (2) or more subjects experience an allergic reaction such as generalized urticaria (defined as occurring at three or more body parts) within 72 hours after administration of light that is considered related to RD19.
- Three (3) or more subjects experience a \geq Grade 3 AE (systemic and/or clinical laboratory abnormality), in the same SOC grouping of Preferred Terms based on the Medical Dictionary for Regulatory Activities (MedDRA) coding, considered to be related to RD19.

Study device use and enrollments may resume only after review of the AEs that caused the pause results.

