 - Reactogenicity assessments will include an assessment of illumination site reactions – erythema, edema/induration, pain and difficulty swallowing, as well as systemic reactions—fever, chills, headache, and nausea. Pre-illumination reactogenicity assessments will be performed immediately prior to first RD19 use to establish a baseline, then the use of the RD19 device will occur.
- Subjects will be observed in the clinic for at least 60 minutes post each RD19 illumination. The illumination site will be examined, post-use reactogenicity assessments will be performed, and any AEs/SAEs will be recorded on the appropriate e-CRF prior to discharge from the clinic. The oropharynx and surrounding tissues will also be examined on Days 1, 7, 14 and during unscheduled visits and early termination visits.
- Vital signs:
- Vital sign measurements will include systolic and diastolic BP, HR, and oral temperature. Vital signs will be measured at timepoints specified in the SOA. On Days 1, 7 and 14, vital sign measurements will be collected prior to device administration. Vital signs assessed on Day 1 prior to the first use of RD19 will be considered as baseline. Subjects must not eat or drink anything hot or cold within 10 minutes prior to taking their oral temperature or using the RD19 device.
- Clinical laboratory evaluations:
 - Fasting is not required before collection of clinical laboratory evaluations.
 - Urine pregnancy test will be performed locally by the site laboratory at the screening visit and at the final study visit. Results must be confirmed as negative prior to randomization on Day 1 and allocation and use of the RD19 device.
 - Clinical screening laboratory evaluations (CMP and CBC (diff) will be performed locally by the site laboratory).
 - Clinical safety laboratory evaluations will be performed locally by the site laboratory.
 - Methemoglobin will be measured prior to use of the device in the clinic and just prior to discharge from the clinic after 1 hour.
 - Blood and urine will be collected at timepoints specified in the SOA.

○ Diary Cards:

- All subjects will complete a Diary Card daily for the entire term of the study. Diary Cards will be reviewed with the subjects for any AEs (solicited injection site and systemic reactions, as well as unsolicited AEs), SAEs and concomitant medications. Diary Cards will be collected at the end of a volunteer's participation in the study.

○ Acceptability Assessment:

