6.2.10 Time Period and Frequency for Event Assessment and Follow-Up

For this study:

- Solicited and Unsolicited AEs will be recorded by volunteers daily on the Diary Card and collected on Clinic visit days 7, 14 and any unscheduled clinical trial unit visits.

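### The third pausing criterion counts allergic reactions with no stated grade, but section 3.1 asks for an immediate call only above moderate intensity, so a milder case at home may reach the site only at the next visit

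*Combined protocol and SAP*

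**What the plan says.** Section 5.5.1 lists four events that pause the study. The third is met when "Two (2) or more subjects experience an allergic reaction such as generalized urticaria" within 72 hours of illumination, if the reaction is considered related to the device. Urticaria is described by extent (three or more body parts), and no severity grade is given. The fourth criterion does set one: it counts subjects with at least a "Grade 3 AE (systemic and/or clinical laboratory abnormality").

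Section 3.1 governs what subjects report between visits. They are to "immediately contact the clinical coordinator and/or the PI in all instances where they experience an AE of greater than moderate intensity". A separate sentence encourages prompt contact "for AEs of a medically urgent nature", and the synopsis (1.1) says much the same. Directly after the above-moderate instruction comes "Volunteers will be instructed to report to the clinical trial unit for an unscheduled visit", or to seek suitable care according to the nature of the event.

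Everything else from non-clinic days goes on the diary card, which under 6.2.10 is "collected on Clinic visit days 7, 14 and any unscheduled clinical trial unit visits". In the clinic, "Subjects will be observed in the clinic for at least 60 minutes post each RD19 illumination" (section 6.2). Section 6.2.2 lists the solicited events; neither urticaria nor allergic reaction is among them. Section 4.3.2 adds that "study staff will contact subjects prior to appointments", as a retention measure.

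**The concern.** A pausing rule works only as fast as its events reach the people who apply it. Here the event that counts and the event that must be phoned in are defined on different scales. The pausing rule uses type and extent of reaction; the call rule uses intensity or urgency. A case can meet the first without meeting the second.

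Two things are at stake. The affected subject may go on using a first-in-man device twice a day while already reacting to it. And because the criterion needs two related cases, a pause that turns on the unreported one is delayed by the same interval. A pause also stops enrollment, and section 4 expects all Day 1 visits within about a week, so several days matter on this trial's timescale. Earlier detection would help other subjects mainly when the case occurs in the first week; by Day 14 most of their exposure is over.

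**Working it through.** The plan states no operating characteristic for the pausing rules, so there is no figure to reproduce. The check compares the rules and then counts days.

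**Does a countable case have to be phoned in?**

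| Feature | Third pausing criterion (5.5.1) | Contact rule (3.1) |
|---|---|---|
| Severity | none stated | above moderate, or medically urgent |
| Type of event | allergic reaction, related to the device | any |
| Time frame | 72 hours after a use | immediate, or prompt if urgent |

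The default scale in 6.2.8 describes a Grade 2 event as one that disturbs daily life without important or lasting risk. Itchy but tolerable hives on three body sites could fit that description. They would count toward the criterion if related, and would not clearly require a call.

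**Do other routes catch it?** Clinic observation covers at least 1 hour of the 72 after a clinic use and none of the time after a home use. No symptom call is scheduled between visits. The pre-appointment contact might bring a reaction to light, but that is not its purpose. The investigator can withdraw a subject (5.5.3) and must attribute the event (6.2.9), but only once it is known.

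**Longest delay.** Inputs: clinic visits on Days 1, 7 and 14 (Table 3, nominal days); two uses per day (Table 4). Delay = next visit day − onset day.

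- Onset after discharge on Day 1: 7 − 1 = 6 days. Onset on Day 6: 7 − 6 = 1 day.
- Onset after discharge on Day 7: 14 − 7 = 7 days. Onset on Day 13: 14 − 13 = 1 day.
- If onset were equally likely on each day, which the protocol does not say, the means would be (6+5+4+3+2+1)/6 = 3.5 days and (7+6+5+4+3+2+1)/7 = 4.0 days.

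**Most further home uses**, taking the clinic use as the first of each visit day:

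- Day 1 to Day 7: 1 + 2 × 5 = 11.
- Day 7 to Day 14: 1 + 2 × 6 = 13.

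**How often could the criterion be met at all?** No reaction rate is given, so a range of true per-subject rates p is assumed. With 25 subjects, P(2 or more) = 1 − (1−p)^25 − 25p(1−p)^24:

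| Assumed p | P(2 or more of 25) |
|---|---|
| 1% | 2.6% |
| 2% | 8.9% |
| 5% | 35.8% |
| 10% | 72.9% |

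These figures ignore reporting delay and cover reactions of all severities. They show only that the criterion is unlikely to be reached if reactions are rare and quite likely to be reached if they are not.

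**The case against.** The strongest reply is that the third criterion does not say it applies at every grade. It is silent, and its one example is a generalized reaction, so an isolated mild patch of rash is not clearly covered. That stands: a reader might infer that every trivial rash counts, and the text does not support that. The point is therefore confined to mild or moderate generalized reactions.

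Second, the governing detail may lie elsewhere. Appendix 2 takes precedence for grading, Appendix 1 holds the user instructions, and the contents list a subject handout and training; none of these is in the text available. If Appendix 2 grades all generalized urticaria as 3 or higher, the gap closes for urticaria but not for other milder allergic reactions. If the handout or user instructions already ask for a call, only 3.1 needs aligning. For the same reason one cannot infer that the plan has no hold for an individual subject: the contents list subject-level pausing criteria that do not appear in the body available.

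Third, the remaining harm is limited. Related laryngospasm, bronchospasm or anaphylaxis within 2 hours pauses the study on a single case, and severe events call for immediate contact. Many people with widespread hives would call anyway, and exclusion 8 in section 4.2 removes those with known severe reactions to nitrates, nitrites or sun. This lowers the likely number of late cases. It does not make the two rules agree.

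**Conclusion.** The mismatch is real and worth correcting. As 3.1 is written, a subject who follows it exactly may leave a countable allergic reaction unknown to the site until the next visit: at most about 6 days after Day 1 or 7 days after Day 7, with at most 11 or 13 further home uses. Those ceilings require onset just after discharge, no call, no unscheduled visit and continued use through symptoms.

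It would go too far to conclude that such cases will be missed for a week, or that the criterion cannot work. Subjects may call or come in of their own accord, no event rate is given, and a pause needs two related cases. Confidence is medium, because the conclusion rests on 3.1 without the appendices and handout.

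**What to change.** In 3.1, add to the immediate-contact instruction: any suspected allergic reaction at any intensity, meaning hives or rash away from the illumination site, swelling of the face, lips or eyelids, or breathing difficulty. The next device use is held until the PI has assessed the subject by phone.

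State that mild or moderate erythema or edema at the illumination site stays on the diary card. These are solicited events under 6.2.2, and a call and hold for any swelling would interrupt dosing for expected local effects.

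Align the handout and Appendix 1. Record any missed use as a PI-directed hold and not as non-compliance, so that the compliance endpoint and per-protocol membership (7.3) are not distorted.

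The cost is a sentence or two in 3.1 repeated in the subject materials, a few extra calls and occasional missed uses. No visits or staff are added, and the pausing criteria stay as they are.
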